Recruitment. We acknowledge the challenge to recruit adults with prediabetes for a nutrition study during this unusual time of pandemic. Consistent with our previous studies,⁵⁰⁻⁵² we will consult the recruitment office of the OSU CCTS for assistance. They maintain a participant database (>126K registrants) and provide marketing support for study recruitment (e.g. social media, printed flyers, e-newsletters reaching ~100K faculty/staff and students at OSU).

[figure not shown]
All proposed procedures are well-established and frequently utilized by our research team. We, therefore, do not expect potential technical problems. However, we acknowledge the challenge of the potential interpersonal variability of dietary responses to WWB among the enrolled study participants, and there may be difficulties to identify sufficient “high-responders” and “low-responders” based solely on the glycemic responses. If needed, we will combine other health parameters, such as HOMA-IR, serum endotoxin, and select inflammatory biomarkers, to define response indicators for their gut microbiome dependency.

V. Significance of the Research and Potential Benefits

Whole grain, especially whole wheat food, is a recognized, important part of healthy dietary patterns due to its high abundance of fibers, protein, and bioactive phytochemicals. However, from both clinical trials and observational studies, controversy persists to clearly define the advantage of having incorporating whole wheat into the diet to manage metabolic disorders including prediabetes. Gut microbial composition and their metabolism, as recently emerged in many exciting studies, may play a critical role in determining the health benefits of having whole wheat in a regular diet in diverse populations. Therefore, our study is **significant** because it will provide critical data to help resolve the controversy by studying the gut microbiome-mediated, personalized effects of whole wheat intake in persons with prediabetes. Specifically, the integration of our multi-omics workflow coupled with studies in humans and in vitro will advance an understanding of the metabolic signatures of gut bacteria function to control the risk of prediabetes/glucose intolerance

VI. Procedures

A. Overview of Study Design

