2. Recruitment. We will recruit participants through posted flyers, e-mail, electronic and newsprint advertisements (e.g. campus student and faculty/staff newspapers, local and regional newspapers; see attachment “*Advertisements*”), and word of mouth. The posted advertisements will instruct interested participants to call the study center ([name] Laboratory, Department of Human Sciences) or complete an online pre-screening survey to obtain further information. During the phone-in hours, a trained individual (i.e. project coordinator or graduate assistant) will be available to describe the study and determine preliminary qualification by conducting a scripted phone interview (e.g. do you take dietary supplements?, do you smoke?; see “*Phone Script*” attachment). The individual will record answers and assess whether the person calling is likely or not to be an acceptable study participant. If the caller and the interviewer agree that the caller should participate, the prospective participant will be invited to a screening meeting, where the study will be fully described, and the individual will be provided a consent form to complete prior to any involvement in the study procedures. Data collected during this phase will include participant’s age, health status, physical activity, and contact information (see “*Informed Consent*” attachment).

3. Power Calculation and Data Analysis. [name] (biostatistician; *co-PI and Dept of Biomedical Informatics*) performed a power analysis. To ensure that the order by which each participant completes each trial is randomized, a random sequence generator (<http://www.random.org/sequences/>) will be used to determine the order by which each participant will undergo the two trials. We will primarily compare the

within-subject changes (WWB endpoint vs. WB endpoint) between high-responders and low-responders. We anticipate to have 6-12 high-responders and 5-10 low-responders of the total 40 study participants to achieve 80% power to detect a 1.6-fold difference in the changes of postprandial glucose levels (AUC from 0 to 180 minutes) between high-responders and low-responders, at the expected coefficient of variation (CV) 0.5 at a significant level of 0.05.

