Mixed effect modeling will be performed, diet and time will be included as fixed factors while participant serves as a random factor. False discovery rate (FDR) will be used to control type I error rate for microbiome and metabolome data, while the Bonferroni method will be applied for other measures (e.g., inflammatory markers). Data will be first normalized before analysis. Spearman correlations will be calculated to define associations between microbes, inflammatory genes, metabolites that show significant changes in highresponders.

To test whether the changes in microbes after WWB intake associate with the biological response, logistic regression will be fitted to each of the potential microbes or as a combination. We will also couple the logistic regression with receiver-operating characteristic (ROC) analysis to evaluate the specificity and sensitivity of the microbes that predict participants' biological response, and the area under the curve (AUC) of the microbial model will be displayed. Data analysis will be performed in R (open resource) or SAS (SAS, Inc; Cary, NC). The sample size was calculated in PASS 20 (NCSS, LLC; Kaysville, Utah).

C. Measurement/Instrumentation

All procedures will take place in the Human Nutrition Program located in Evans Laboratory. Infrastructure that is present includes a metabolic research kitchen, a private office to meet with participants, a clinical research laboratory for performing phlebotomy and research procedures, and a separate biochemical laboratory for processing and preserving biological specimens.

1. *Anthropometric Parameters and Blood Pressure.* At screening, day 1, 7, and 14, participants will rest for 15 minutes prior to determining blood pressure using an automated blood pressure cuff. BMI will be calculated from height determined from a wall-mounted stadiometer and weight from a calibrated scale.

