6. *Gut Permeability.* On day 14 of each intervention, fasted participants will ingest a glucose solution (75 g; oral glucose tolerance test) containing 4-sugar probes [lactulose (5 g), mannitol (1 g), sucralose (1 g), and erythritol (1 g)] as described.^{59, 60} Urinary sugars will be assessed by LC-MS as we established.⁵⁹ Sugar excretion (%), and excretion ratios of sugars from 0-5 h (lactulose/mannitol) and 6-24 h (sucralose/erythritol) will be calculated to reflect upper and lower gastrointestinal permeability, respectively.⁶¹⁻⁶⁴ This approach is based on lactulose being absorbed in the small intestine, but not the colon, whereas sucralose is absorbed in the colon.⁶⁵ Thus, these studies will define site-specific gut permeability, and the benefit of WWB treatment.

7. *Microbiota Composition.* Microbiota composition and the predicted functional metagenome will be assessed from fecal samples provided on day 14 of each intervention arm as previously described.⁶⁶⁻⁷⁰ Effects of WWB (vs WB) on total bacterial abundance will be determined by qPCR.⁷¹ Microbiota will be characterized for diversity and community structure by sequencing 16S rRNA genes using MiSeq. Bacteria will be identified by comparing sequences representing each operation taxonomic unit (OTU) with RDP and Silva databases.^{72, 73} α -Diversity (OTU richness, Shannon-Wiener diversity index, evenness) will be calculated using Qiime. Comparisons of diversity among samples (β -diversity) will be performed using the Bray-Curtis dissimilarity,⁷⁴ followed by multivariate analyses (e.g. principle coordinate analysis, permutational multivariate analysis of variance, analysis of similarity, partial least square discriminant analysis). The functional metagenome will be predicted using PICRUSt⁷⁵ and PanFP⁷⁶ based on reference genome databases and the KEGG Orthology classification scheme to obtain a functional gene abundance matrix.

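### The microbial ROC results (AUC, sensitivity, specificity) have no stated internal validation, so as written they are expected to look too favourable once taxa are screened or combined

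*Combined protocol and SAP*

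**What the plan says.** Section VI.B.3 gives the purpose of the analysis: "To test whether the changes in microbes after WWB intake associate with the biological response". The method is that "logistic regression will be fitted to each of the potential microbes or as a combination". ROC analysis is then coupled to these fits to assess the sensitivity and specificity of microbes that predict response, and "the area under the curve (AUC) of the microbial model will be displayed".

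Three further statements bear on the point:

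- **Error control (VI.B.3).** "False discovery rate (FDR) will be used to control type I error rate for microbiome and metabolome data". This is not made an entry rule for the logistic models. The one significance filter in that section, "metabolites that show significant changes in highresponders", belongs to the Spearman correlations.
- **Group sizes (VI.B.3).** "We anticipate to have 6-12 high-responders and 5-10 low-responders of the total 40 study participants". Section IV, Pitfalls and Alternatives, adds that "there may be difficulties to identify sufficient" high- and low-responders, so the low end is realistic.
- **Source of taxa (VI.C.7).** "Microbiota will be characterized for diversity and community structure by sequencing 16S rRNA genes using MiSeq", with bacteria identified by operational taxonomic unit. The number of candidate taxa is not given.

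No section mentions cross-validation, bootstrapping or held-out data for the ROC model. Section VI.F, Internal Validity, concerns the coding of samples and records. The permutational and discriminant methods in VI.C.7 concern beta-diversity.

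**The concern.** An AUC computed on the data used to pick and fit the predictors measures how well the model describes those participants, not how well it would classify new ones. The gap widens with fewer participants and with more predictors tried or combined. The plan allows both per-taxon fits and combinations, in perhaps 11 to 22 people.

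The study sets out to learn whether gut bacteria explain who benefits from whole wheat bread (II.D, III). The ROC figures are where the plan expresses how well microbes predict response. If they can look good on noise, a reader cannot tell a useful microbial signature from an accident of selection.

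**Working it through.** **Inputs from the documents.** Groups of 6–12 high- and 5–10 low-responders out of 40 (VI.B.3). If all 40 are modelled as high-responders against the rest, the splits run from 12 v 28 (40 − 12) to 6 v 34 (40 − 6). The plan states no AUC, candidate count or sample size for the ROC model, so there is no figure of its own to reproduce. The 80% power statement concerns the glucose comparison and is not used here.

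**Assumptions, not in the documents.** 1, 6, 20 or 100 candidate taxa; normally distributed values; independent taxa, or a common correlation of 0.6; no false-discovery gate unless stated.

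**Step 1. One noise taxon, by formula.** On noise the AUC has mean 0.50 and SD = √[(n₁+n₂+1)/(12·n₁·n₂)]. If the direction is fixed beforehand, the AUC is unbiased. If the direction is fitted, the apparent AUC is max(AUC, 1 − AUC), with mean about 0.50 + 0.798 × SD, where 0.798 = √(2/π).

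- 12 v 10: SD = √(23/1440) = 0.126; mean 0.50 + 0.101 = 0.60.
- 6 v 5: SD = √(12/360) = 0.183; mean 0.50 + 0.146 = 0.65.
- 12 v 28: SD = √(41/4032) = 0.101; mean 0.50 + 0.080 = 0.58.
- 6 v 34: SD = √(41/2448) = 0.129; mean 0.50 + 0.103 = 0.60.

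**Step 2. Best single taxon of several, pure noise (true AUC 0.50), by simulation.** Mean apparent AUC:

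| Groups | Correlation | 1 | 6 | 20 | 100 |
|---|---|---|---|---|---|
| 12 v 10 | 0 | 0.60 | 0.71 | 0.77 | 0.83 |
| 12 v 10 | 0.6 | 0.60 | 0.69 | 0.73 | 0.78 |
| 6 v 5 | 0 | 0.65 | 0.80 | 0.88 | 0.96 |
| 12 v 28 | 0 | 0.58 | 0.67 | 0.72 | 0.77 |
| 6 v 34 | 0 | 0.60 | 0.71 | 0.77 | 0.84 |

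The first column agrees with Step 1. At 12 v 10, the chance that noise alone gives an apparent AUC of 0.80 or more with 6, 20 or 100 candidates is 9%, 29% or 82% if independent, and 8%, 17% or 38% at correlation 0.6.

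**Step 3. Combinations, pure noise, 12 v 10, independent taxa.** Three pre-specified taxa give a mean apparent AUC of 0.69, and five give 0.76. The best three of 20 or of 100 give 0.86 or 0.93. Leave-pair-out validation that repeats the selection inside each split returns 0.50, as do new data.

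**Step 4. One real taxon (true AUC 0.70) among noise taxa, best single taxon chosen, 12 v 10, independent.**

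| Candidates | 1 | 6 | 20 | 100 |
|---|---|---|---|---|
| Apparent AUC | 0.70 | 0.75 | 0.79 | 0.84 |
| True AUC of the chosen taxon | 0.68 | 0.60 | 0.57 | 0.53 |
| Gap | 0.02 | 0.15 | 0.22 | 0.31 |

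The true value is 0.68 with one candidate because the fitted direction is sometimes wrong. As candidates increase, the apparent figure rises while real performance falls.

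**Step 5. If a false-discovery gate controls entry (5% Benjamini-Hochberg on high v low, assumed), 12 v 10.** On pure noise some taxon enters in about 5% of datasets. When one does, the mean apparent AUC for 6, 20 or 100 candidates is 0.85, 0.88 or 0.92. A real taxon with true AUC 0.70 passes in 16%, 8% or 3% of datasets, and then shows 0.86, 0.89 or 0.93.

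**The case against.** The strongest reply is that the analysis tests association, microbiome data are under false-discovery control, and the AUC is only displayed alongside. If that control gates entry, noise taxa rarely reach the model. Much of this stands. The stated purpose is association, and a gate would cut false entry to about 5% of datasets. But the plan does not say that a gate applies, the same section speaks of prediction, and a gate does not correct the AUC of a taxon that passes (Step 5).

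A second reply is that the size rests wholly on assumed candidate numbers, correlation and distribution. That also stands. The direction of the bias follows from the method, but its size is a range, and correlated taxa reduce it.

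A third is that a validated AUC from 6 v 5 says little. That is true: on noise, leave-pair-out AUCs there have an SD of 0.23–0.25. Validation removes the bias but cannot supply precision.

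A reader might infer that modelling all 40 participants removes the problem. The group sizes in VI.B.3 do not support this: 6 v 34 behaves almost like 12 v 10. Nor can a single pre-specified taxon always be taken as free of bias; on noise with a fitted direction it averages 0.60 at 12 v 10 and 0.65 at 6 v 5.

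**Conclusion.** The concern holds. As written, the AUC, sensitivity and specificity are expected to be too favourable whenever taxa are screened or combined. Under the assumptions above, with 6 to 100 candidates and no gate, a noise taxon chosen as best shows a mean AUC of 0.69–0.83 at 12 v 10 (across correlation 0 and 0.6) and 0.80–0.96 at 6 v 5 (independent taxa). The distortion is small for one pre-specified taxon with real signal (0.70 against 0.68 at 12 v 10) or with its direction fixed beforehand. Confidence is high in the omission and moderate in the size.

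Stronger readings go beyond the documents. The plan does not exclude validation; it is silent. The AUC is not the primary comparison, which is the within-participant glucose change between responder groups. It is not the only planned measure of prediction either, since sensitivity and specificity stand in the same sentence. The undefined candidate list and entry rule are missing detail that makes the size uncertain; stating them would not by itself correct an AUC scored on its own fitting data.

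**What to change.** In VI.B.3, make an internally validated AUC the main reported figure, for example by leave-pair-out, with taxon selection and any false-discovery gate repeated inside every split. Leave-pair-out suits these sizes; with five low-responders, stratified five-fold would hold out only one per fold. Take sensitivity and specificity from held-out predictions. Add a label-permutation reference that reruns the whole procedure. Label any same-sample AUC as apparent, and describe the result as exploratory if the groups are near 6 v 5.

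The cost is more analysis code and no new data. The reported AUC will be lower and imprecise. On noise, the leave-pair-out AUC has an SD of 0.20–0.23 and a 95th percentile of 0.79–0.89 at 12 v 10; at 6 v 5 the 95th percentile is 0.83–0.93, so the figure there is nearly uninformative. The permutation reference would make that visible to the reader.

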
C. Gut microbial diversity may explain the personalized protective effects of whole wheat against prediabetes. As evident by the sharp incline in the prevalence of prediabetes, blood glucose levels are rapidly increasing in the worldwide population. It is estimated that impaired glucose tolerance will affect at least 37% of the adult population in the US alone.²⁷ Prediabetes, characterized by chronically impaired blood glucose responses, is a significant risk factor for type II diabetes mellitus (T2DM), with up to 70% of prediabetics eventually developing the disease.²⁸ It is also linked to other manifestations, collectively termed metabolic syndrome, including obesity, hypertension, non-alcoholic fatty liver disease, hypertriglyceridemia, and cardiovascular disease.²⁹ Thus, maintaining normal blood glucose levels is considered critical for preventing and controlling metabolic syndrome.

D. Summary. This overview demonstrates that consumption of whole grain foods has been associated with decreased risk of obesity, prediabetes, and type 2 diabetes.^{1, 30-32} However, mechanisms mediating the protective effect of whole grains are unclear, although glycemic response and insulin sensitivity are the most common mechanisms suggested by epidemiological studies.³³⁻³⁶ An early report has raised the possibility of gut microbiome-mediated effects linking cereal fiber consumption with decreased risk of T2DM;³⁷ this knowledge gap continues to persist. It was suggested that modifications in gut microbiota, gut fermentation, and influences of yet unknown molecular factors such as phytochemicals may affect insulin sensitivity and further development of type 2 diabetes. Recent results suggest a link between changed gut microbiota and varied glycemic responses.^{1, 13, 14} Furthermore, subjects with T2DM had depleted *Bifidobacteria*,³⁸ and also the level of glucose tolerance was associated with certain gut bacteria.³⁹ Another review concluded that despite convincing epidemiological evidence, *the lack of controlled clinical studies to support or explain the mechanisms underlying the protective effect of whole grains against type 2 diabetes.*⁴⁰ Thus, this application **aims to uncover** the role of gut microbiota and their metabolites of whole wheat bread (WWB) components in mediating blood glucose excursions in prediabetes. We will

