We plan to conduct a 2x2 *randomized, controlled, crossover trial* in persons with prediabetes (n = 40; 1:1 M/F) to assess 2-wk consumption of white bread (WB) vs whole wheat bread (WWB) on cardiometabolic and gut microbiome parameters (Figure 1). Participants will be recruited from the Columbus, OH area,

consistent with earlier successful studies conducted by the [name] lab. Participants will be block-randomized in 4-unit blocks to receive WB or WWB (128 g/day; 4 bread slices/d, according to the USDA “My Plate” recommendation and other similar studies)^{14, 53, 54} for 2-wks. During each study arm, participants will be provided standardized test meals containing WB or WWB, these foods will be prepared and packaged in the Human Nutrition Metabolic Research Kitchen (Evans Laboratory) to be devoid of whole grain products, probiotic-containing foods (e.g., yogurt), or fermented foods that are known to alter gut bacteria populations. Before and after each 2-wk study arm, a fasting blood sample will be obtained for metabolomic and clinical measures. Blood pressure and anthropometrics also will be assessed on days 1, 7, 14, and participants will collect a fecal sample to provide to the study team during their visits on day 1 and day 14. Lastly, on day 14, participants will simultaneously complete an oral glucose tolerance test and gut permeability test, which involves ingesting a glucose solution that also contains non-digestible sugar probes prior to collecting complete 24-hour urine samples for assessments of upper and lower gut permeability (described below). Upon completing these procedures, participants will undergo >2-weeks wash-out before repeating the study identically, but with crossover to the alternate bread diet.

B. Study Subjects

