2-1/4" (14.6 × 8.3 × 5.7 cm) loaf pan and fermented for 52 min at 30 °C and 85 % relative humidity, then proofed for 25 min, again for 33 min and punched between proofs. Finally, the dough will be baked at 215 °C (Doyon convection oven, Menominee, MI) for 17 min. The bread in this study will be made with limited ingredients to focus on the influence of endogenous chemistry in whole wheat flour on health activity of whole wheat bread.

5. *Dietary Control.* To improve diet homogeneity and limit potential confounding effects of whole grain/wheat intakes on study outcomes, participants' basal diets will be rigorously controlled during each 2-wk intervention by a registered dietitian ([name]) to provide 50-60% energy from carbohydrate, 25-35% fat, and 15-25% protein consistent with the typical American dietary pattern. Participants will be required to consume bread-containing test meals at breakfast and lunch each day; these will be consumed at the study center 4 d/wk during each 2-wk study arm to establish rapport and ensure compliance to study procedures. The WB and WBB used in this study will be prepared in the pilot lab in the Department of Food Science and Technology under the auspice of [name] (co-investigator of the project) to ensure compositional consistency.

Participants' basal diets, including bread-containing test meals, will be administered in a eucaloric manner by estimating energy requirements using the Harris-Benedict equation,⁵⁸ with appropriate adjustment for physical activity.⁴⁵ During each 2-wk study arm, participants will return any uneaten foods, which will be weighed to determine actual energy and nutrient intakes using NDSR dietary analysis software. All foods and beverages will be identical between study arms with the exception of WBB and WB. Participants will also complete a food diary to record the consumption of any non-prescribed foods. Non-fasting body weight will be measured 3 times/week throughout the study to monitor weight stability. If body mass fluctuates >1 kg, the participant's prescribed energy intake will be adjusted to prevent additional weight loss or gain. Thus, our approach will minimize participant burden while applying sufficient dietary rigor to test the hypothesis that WBB consumption, principally through its bioactive phytochemicals, improves glucose tolerance in a microbiota-mediated manner.

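### The microbe–response models contain microbes only; since high versus low response is not randomised, add baseline fasting glucose and a clinical-only benchmark

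*Combined protocol and SAP*

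**What the plan says.** Section VI.B.3 states the aim as "To test whether the changes in microbes after WWB intake associate with the biological response". For this, "logistic regression will be fitted to each of the potential microbes or as a combination", followed by ROC analysis in which "the area under the curve (AUC) of the microbial model will be displayed". No covariate is named for these models and no model without microbes is planned. The only model terms named in the section belong to the separate mixed model, where "diet and time will be included as fixed factors while participant serves as a random factor".

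On group sizes the same section says: "We anticipate to have 6-12 high-responders and 5-10 low-responders of the total 40 study participants to achieve 80% power". Section III says the study is designed to define high- and low-responders rather than to show a mean difference between breads. The end of II.D adds a comparison of gut microbiota composition between those who improved on WWB and those who responded least.

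Three other places bear on the point. II.D reports that "the level of glucose tolerance was associated with certain gut bacteria". VI.A randomises participants "to receive WB or WWB (128 g/day; 4 bread slices/d", the same amount for everyone, while VI.C.5 says the whole diet "will be administered in a eucaloric manner by estimating energy requirements" for each person. VI.C.2 measures fasting glucose at screening, day 1 and day 14, and fasting insulin at days 1 and 14; the oral glucose tolerance test is on day 14 only.

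**The concern.** Randomisation and the crossover protect the comparison of WWB with WB within a person. They do not protect the comparison of people who respond with people who do not. Such people may differ in starting glycemia, sex or body size, and any of these could be related to the room for improvement and to the gut flora. The protocol itself reports a link between glucose tolerance and certain bacteria.

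The trial wants to say that gut bacteria explain who benefits. A microbial ROC AUC shown alone cannot separate that from the simpler account that fasting glucose, already measured at screening, would have sorted participants as well. FDR control limits the number of chance findings among many taxa; it does nothing about an association that is real but runs through a third variable.

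**Working it through.** **Group sizes.** The plan's power figure reproduces only at the top of its range. Take a reference mean of 1, a difference of 0.6 (1.6-fold), SD 0.5 and two-sided 0.05. At 12 v 10, SE = 0.5 × √(1/12 + 1/10) = 0.214, and power = Φ(0.6/0.214 − 1.96) = 0.80. At 6 v 5, SE = 0.303 and power = 0.51. The present point does not depend on this, but both group sizes are carried through below.

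**Simulation of confounding.** Inputs from the plan: N = 40, with the extremes of response taken as 12 v 10 or 6 v 5. Assumed: a baseline factor X has correlation r with the response and the same r with a microbial measure that has no link of its own to response. The induced microbe–response correlation is r × r. Each microbe is tested at nominal 5% by a t-test between the extreme groups. Repeat runs of 4,000 to 6,000 trials differed by a point or two.

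| r (both paths) | r × r | 12 v 10 | 6 v 5 |
|---|---|---|---|
| 0.2 | 0.04 | 5% | 5–6% |
| 0.3 | 0.09 | 7–8% | 6–7% |
| 0.4 | 0.16 | 14% | 11–12% |
| 0.5 | 0.25 | 27–28% | 22–24% |

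Unequal paths give less: r = 0.2 on one and 0.4 on the other gives about 7%.

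**ROC AUC.** At r = 0.5 the unlinked microbe has a mean apparent (direction-free) ROC AUC of 0.68 at 12 v 10 and 0.73–0.74 at 6 v 5. With no confounding at all the values are already 0.60 and 0.65. At r = 0.5 and 12 v 10, X alone averages 0.82, so a clinical-only benchmark would reveal what the microbial curve alone cannot.

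**Does adjustment work?** It depends on the model.

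- Logistic, adjusted for X only: about 7–8% false positives at 12 v 10 and 11–14% at 6 v 5. Part of this is small-sample error, since the unadjusted logistic test with no confounding already gives about 7% and 8.5%.
- Logistic, adjusted for X, sex and body size: four slopes, so 10/4 = 2.5 or 5/4 = 1.25 low-responders per slope. False positives are 9–12% at 12 v 10. At 6 v 5 they are 18–20%, with separation in 28–73% of runs.
- Linear model of the continuous response in all 40: unadjusted, 8% at r = 0.3 and 35% at r = 0.5. Adjusted for X, 4–6% throughout; with two further covariates added, 4.6–5.2%. Using everyone does not itself remove the bias; the covariate does.

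**Relative bread dose.** Weight = BMI × height². For BMI 30–35 (VI.B.1) and assumed heights of 1.55–1.88 m, weight runs from 30 × 1.55² = 72.1 kg to 35 × 1.88² = 123.7 kg. Then 128 g/day is 1.78 to 1.03 g/kg, a 1.7-fold range. At assumed intakes of 1,600–3,000 kcal/day it is 80 to 43 g per 1,000 kcal, a 1.9-fold range. Targeting BMI does not make relative dose uniform.

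**The case against.** The strongest reply is that the named predictor is the change in microbes after WWB. A taxon whose level merely follows glycemic severity is present in both arms and largely cancels. That stands, and it rules out the reading that any microbe tracking severity will pass for a determinant of response. It does not remove the point: a change that itself depends on baseline glycemia or relative dose does not cancel, and II.D also plans a comparison of composition, to which the reply does not apply.

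Second, the design narrows the range. VI.B.1 sets fasting glucose at 100–125 mg/dL and targets BMI 30–35, and VI.C.5 controls the diet. This makes r = 0.5 on both paths harder to defend. The restriction is partial, because the screening section (VI.D.2) applies eligibility as a best fit and fasting glucose does not fix insulin resistance.

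Third, a reader might infer that an ROC AUC near 0.7 would be mostly confounding. The no-confounding values of 0.60–0.65 show that much of it would be small-sample optimism.

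Fourth, adjustment can go too far. II.D also raises the possibility that gut microbiota affect insulin sensitivity. If microbes influence baseline glycemia, conditioning on it removes part of the effect under study. That stands and shapes the fix.

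Fifth, nothing in the documents links relative bread dose to response or to microbial change, and each person receives the same bread amount and glucose load in both arms. Dose belongs in a sensitivity analysis.

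**Conclusion.** The omission is plain in the text: the logistic and ROC models hold microbes only, have no clinical benchmark, and serve the trial's central, non-randomised contrast. The consequence is conditional. It requires a baseline factor related both to response and to the microbial measure used, and the documents give no correlation for either path. Under equal assumed correlations the excess over 5% is negligible to small up to r = 0.3, moderate at 0.4 (11–14%) and large at 0.5 (22–28%).

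The documents do not support the stronger statement that microbial findings will be spurious. Nor does the point touch the randomised WWB v WB comparison. It is a cheap improvement that the plan should make, not a fatal flaw.

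**What to change.** 1. As the main microbe–response analysis, or beside the logistic model, regress the continuous WWB–WB difference in glucose AUC (0–180 min) in all 40 participants on each microbial measure. Prespecify pre-intervention fasting glucose as the covariate. A baseline glucose-tolerance value is not available, because that test is done only on day 14.
2. Say which microbial measure is meant, change or composition, and use sex and either body weight or bread per kcal as sensitivity covariates.
3. Report the ROC AUC of a clinical-only model next to that of the microbial model, with the cross-validated gain from adding microbes.
4. Show unadjusted and adjusted results together, because of the over-adjustment risk.
5. Do not put several unpenalised covariates into the logistic model of 6–12 v 5–10.

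The cost is analysis wording: fasting glucose, weight, sex and actual energy intake are already recorded or known. The statistical price is one or a few degrees of freedom and a gain in ROC AUC that will be imprecise with 11–22 people in the extreme groups.
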